**Sleep Disturbance in Hong Kong Children with Cancer: A Cross-Sectional Study
Comparing Healthy Counterparts and Children with Other Chronic Diseases**

RESEARCH PROTOCOL

[name], HKCH WM(Paed)

Table of Contents

Content	Page
Abstract	2
1. Introduction	2
1.1 Sleep Disturbances in Children with Cancer	2
1.2 Comparison with Healthy Children and Other Chronic Illnesses	3
2. Study Objectives	3
3. Study Significance	3
4. Methods	3
4.1 Study Design	3
4.2 Data Collection	4
4.2.1. The Chinese version of Pittsburgh Sleep Quality Index (PSQI)	4
4.2.2. The Chinese version of Pediatric Quality of Life Inventory 4.0 (PedsQL 4.0)	4
4.3 Key Variables	5
4.3.1. Primary Outcome Variable	5
4.3.2. Secondary Outcome Variable	5
4.3.3. Demographic Variables	5
4.4 Expected Outcomes	5
4.4.1. Children with Cancer	5
4.4.2. Children with Other Chronic Illnesses	5
4.4.3. Healthy Children	6
5. Study Population	6
5.1 Children with Cancer (n=50)	6
5.2 Children with Other Chronic Illnesses (n=50)	6
5.3 Healthy Children (n=50)	7
5.4 Exclusion Criteria	7
6. Procedure	7
7. Statistical Analysis	7
8. Parental Consent and Children's Assent	8
8.1 Parental Consent	8
8.2 Children's Assent	8
9. Ethical Approval	9
10. Data Handling and Record Keeping	9
11. Ethical Considerations	
References	10

Sleep Disturbance in Hong Kong Children with Cancer: A Cross-Sectional Study Comparing Healthy Counterparts and Children with Other Chronic Diseases

Version No. and Date: Version 4, 6th June, 2025

Principal Investigator: [name], Ward Manager, Department of Paediatrics and Adolescent Medicine, Hong Kong Children's Hospital

Abstract

Sleep disturbances are prevalent among children with chronic illnesses, yet the specific impact of cancer on sleep remains underexplored. This prospective and cross-sectional study aims to evaluate the prevalence, severity, and characteristics of sleep disturbances in Chinese children with cancer compared to healthy peers and children with other chronic diseases. By leveraging validated sleep assessment tools and parental reports, the goal is to identify unique challenges faced by children with cancer. Results might influence the design of personalized interventions aimed at enhancing the overall well-being of children with cancer.

1. Introduction

Sleep stands as a fundamental foundation for children's health as it supports physical state, emotional stability, and cognitive performance of children (Baddam & Nasser, 2021). Adequate sleep throughout childhood remains vital because it promotes physical development, strengthens immune functions, and facilitates memory consolidation (Paruthi et al., 2016). Chronic illness patients show a heightened risk of sleep disturbances, particularly cancer children, who experience these disturbances due to a combination of psychological and physiological and environmental factors (Lee et al., 2017).

1.1 Sleep Disturbances in Children with Cancer

Research data shows a high incidence of sleep disturbances affecting children treated for cancer since studies demonstrate a wide range from 40% to 80% (Ho et al., 2022; Kaushik et al., 2022; Sheikh et al., 2021). Sleep disruptions in children stem from various sources. Physiological side effects of cancer like pain along with nausea and fatigue emerge as vital factors that disrupt children during cancer treatment (Gedaly-Duff et al., 2006; Zupanec et al., 2017). The sleep issues get worse when cancer patients use corticosteroids and chemotherapy drugs since these medications disrupt the body's natural sleep-wake pattern (Hinds et al., 2007). External hospital factors amplify the existing sleep disturbances in pediatric cancer patients. Medical procedures frequently interrupt pediatric patients in hospital beds during nighttime hours, while ambient noise and bright lighting in the setting contribute to significant barriers to restful sleep (Perdikaris et al., 2009). The combination of internal factors and hospital environment elements prevents pediatric cancer patients from experiencing adequate sleep quality.

1.2 Comparison with Healthy Children and Other Chronic Illnesses

In contrast, healthy children generally experience more consistent and undisturbed sleep accentuates how chronic illnesses combined with hospitalization damage children's sleep quality. Children with other chronic illnesses also encounter sleep difficulties yet their reasons for these issues differ from those diagnosed with cancer. For instance, the condition of asthma triggers nighttime awakenings because of wheezing and coughing, while diabetic patients experience disrupted sleep due to fluctuating glucose levels (Adavadkar et al., 2022; Meltzer & Mindell, 2017). These conditions cause sleep interference but patients tend to experience less psychological and physical distress from cancer which leads to milder overall sleep issues.

2. Study Objectives

The objectives of this study are threefold:

- 1) To assess the prevalence and nature of sleep disturbances in children with cancer.
- 2) To compare sleep disturbances in children with cancer to those in healthy children and children with other chronic diseases.
- 3) To identify potential factors contributing to sleep disturbances in paediatric patients.

3. Study Significance

This study contributes to the comprehension of pediatric sleep disturbances by carefully evaluating sleep disruptions among three groups: children with cancer, children with other chronic illnesses, and healthy children. The data generated from this study provides vital information for developing targeted therapies specific to population groups with linked sleep disturbance factors. By pinpointing specific contributors, such as hospital environment, medication effects, or pain, the research will lay the groundwork for targeted interventions. These could include reducing nighttime disruptions, refining pain management, or designing sleep-friendly hospital settings. Furthermore, integrating tools like the Chinese version of PSQI into routine care could enable early detection and management of sleep issues, mitigating long-term risks like cognitive and emotional deficits

Beyond oncology, the study's comparison with children who have other chronic illnesses will reveal how different conditions uniquely disrupt sleep, guiding tailored strategies for diverse patient groups. The healthy control group will establish a benchmark for normal sleep, highlighting the extent of disruption caused by chronic illness and elevating sleep as a priority in pediatric care.

4. Methods

4.1 Study Design

A prospective and cross-sectional study will be conducted to examine and compare sleep problems in three groups of children: 1) healthy children, 2) children with various chronic illnesses and undergoing active treatment, and 3) children with cancer and undergoing active treatment. This research design allows for a one-time analysis of sleep characteristics and factors that contribute to disturbances in

three pediatric groups. The study aims to reveal distinct sleep disturbance characteristics of each examined group to determine how sleep changes relate to cancer and other medical conditions among individuals. Such research design allows effective assessment through simultaneous analysis to acquire an in-depth overview of sleep health dynamics among all groups.

4.2 Data Collection

This study will employ objective tools to comprehensively assess sleep disturbances and related outcomes across the three groups: children with cancer, children with other chronic illnesses, and healthy children.

4.2.1 The Chinese version of Pittsburgh Sleep Quality Index (PSQI)

The PSQI is a widely validated self-report questionnaire designed to evaluate sleep quality and disturbances (Mollayeva et al., 2016). Although originally developed for adults, it has been adapted and used effectively in pediatric populations with parental assistance for younger children (De La Vega et al., 2015; Tietze et al., 2014). The Chinese version of the PSQI, as validated for use in Hong Kong Chinese populations, including childhood cancer survivors, retains the same structure as the original PSQI (Ho et al., 2021). The PSQI consists of 19 self-rated questions and 5 questions rated by a bed partner or roommate. The 19 self-rated questions are grouped into 7 component scores: subjective sleep quality, sleep latency, sleep duration, habitual sleep efficiency, sleep disturbances, use of sleep medication, and daytime dysfunction. Each component is scored from 0 to 3, contributing to a global score ranging from 0 to 21. The Chinese version of the PSQI is completed by parents for younger children (e.g., aged 6-11) or by children aged 12-18 with parental assistance if needed. The PSQI's multidimensional approach will provide detailed insights into specific aspects of sleep disruption, such as prolonged sleep onset or frequent awakenings, particularly relevant to hospitalized children with cancer.

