4.2.2 The Chinese version of Pediatric Quality of Life Inventory 4.0 (PedsQL 4.0)

The PedsQL is a well-established instrument for assessing health-related quality of life in children and adolescents aged 2-18 years (Varni et al., 2005). This study will use the Chinese version of PedsQL 4.0 Generic Core Scales, which include 23 items across four domains: physical functioning (8 items), emotional functioning (5 items), social functioning (5 items), and school functioning (5 items). Responses are scored on a 5-point Likert scale (0 = never a problem, 4 = almost always a problem), then transformed to a 0-100 scale, where higher scores reflect better health-related quality of life. The PedsQL yields a total scale score (average of all 23 items), a physical health summary score (average of the 8 physical functioning items), and a psychosocial health summary score (average of the 15 items across emotional, social, and school functioning domains). These scores provide a comprehensive assessment of overall quality of life and specific physical and psychosocial

health outcomes, enabling exploration of how sleep disturbances correlate with broader well-being in children with cancer, other chronic illnesses, and healthy controls. Parent-proxy reports for younger children and self-reports for older participants, mirroring the PSQI administration. The PedsQL 4.0 Generic Core Scale has undergone cross-cultural adaptation into Chinese and psychometric validation, rendering it suitable for application in clinical settings (Ji et al., 2011; Yeung et al., 2012). The Chinese version of PedsQL will serve as a secondary measure to explore how sleep disturbances correlate with broader quality-of-life outcomes, such as fatigue-related physical limitations or emotional distress, which are particularly pertinent to children with chronic illnesses like cancer.

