4.3 Key Variables

4.3.1 Primary Outcome Variable

Sleep quality, measured by the global PSQI score, will be the primary endpoint. This encompasses the seven component scores (e.g., sleep duration, latency, efficiency), providing a holistic assessment of sleep health. A global score >5 will classify participants as having poor sleep quality, enabling prevalence comparisons across groups.

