4.3.3 Demographic Variables

To control for potential confounding effects on sleep patterns and access to healthcare resources, the following demographic and clinical variables will be collected: age (in years), gender, socioeconomic status (SES), disease type, disease status, and use of hypnotics (yes/no). SES will be assessed through parental education (categorized as primary or below, junior secondary, senior secondary, or university/college and above). For children with cancer, disease type (e.g., leukemia, lymphoma, brain tumor, bone tumor, or others) and disease status (e.g., stage 1-4, recurrence, years since diagnosis, treatment type such as chemotherapy, radiotherapy, surgery, immunotherapy, transplant, or combination) will be recorded. For children with other chronic illnesses, disease type (e.g., asthma, type 1 diabetes, chronic kidney disease) will be noted. These factors may influence sleep outcomes, e.g., older children may report greater daytime dysfunction, or lower parental education level may limit access to supportive care, necessitating adjustment in statistical analyses to isolate the effects of chronic illness on sleep quality.

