4.4.3 Healthy Children

Healthy children are expected to demonstrate the highest sleep quality among the three groups, with results showing near-optimal sleep duration and efficiency. Reported data are anticipated to reflect low levels of sleep disturbances, with the majority of children scoring below the clinical threshold on the PSQI. These findings will provide a baseline for understanding how chronic illnesses and hospitalization affect sleep outcomes.

5. Study Population

This study will enroll Chinese children aged 6 to 18 years, divided into three distinct groups based on their health status: children with cancer, children with other chronic illnesses, and healthy children. A total sample size of 150 participants (50 per group) will be targeted to ensure adequate statistical power for comparative analyses. Recruitment will occur at Hong Kong Children's Hospital or the cancer and chronic illness groups, and healthy children will be recruited from healthy siblings of participants or the healthy children of hospital staff with specific inclusion and exclusion criteria applied to each group to maintain homogeneity and minimize confounding variables.

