8.2 Children's Assent

In addition to parental consent, age-appropriate assent will be sought from children aged 6 years and older, recognizing their capacity to understand and agree to participate in research. The assent process will be tailored to the child's developmental stage and health condition. For children with cancer or other chronic illnesses, who may be more familiar with medical contexts, the explanation will be sensitive to their experiences while remaining concise and engaging. Research staff will use simple, age-appropriate language to describe what participation involves, including answering questions about sleep through their parents/legal guardians or research staff. They will be reassured that there are no needles or painful procedures, that they can stop at any time, and that their decision will not impact their treatment or care. Assents will be documented via a signature or verbal confirmation, depending on the child's ability and preference, ensuring that their willingness to participate is respected. If a child expresses reluctance or distress, even with parental consent, their participation will be discontinued to prioritize their well-being.

9. Ethical Approval

This study will adhere to the highest ethical standards governing research involving human participants, particularly vulnerable populations such as children. Prior to commencing data collection, ethical approval will be sought from the Hospital Authority Central Institutional Review Board (IRB), ensuring that the study design, recruitment procedures, and data handling practices align with regulations and ethical guidelines. The IRB review will assess the study's potential risks and benefits, with a focus on minimizing any discomfort or burden to participants, especially given the involvement of children with serious illnesses like cancer. Informed consent will be obtained from parents or legal guardians of all participants, and age-appropriate assent will be sought from children aged 6 years and older, following best practices for pediatric research (Katz et al., 2016). Participants and their families will be fully informed about the study's purpose, procedures, voluntary nature, and their right to withdraw at any time without consequence to their medical care.

10. Data Handling and Record Keeping

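### The PSQI respondent switches from parent to child within the age range on a loose rule, respondent and help are not listed for recording, and the group ANOVA has no age term

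*Protocol*

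**What the plan says.** Protocol section 4.3.1 sets the endpoint: "Sleep quality, measured by the global PSQI score, will be the primary endpoint". A cut-off on the same score (above 5) defines poor sleep.

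Section 4.2.1 describes the instrument: "The PSQI is a widely validated self-report questionnaire designed to evaluate sleep quality and disturbances". It then says that it "is completed by parents for younger children (e.g., aged 6-11) or by children aged 12-18 with parental assistance if needed". Ages 6-11 are only an example, and no criterion is given for when an adolescent needs help.

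Section 4.2.2 covers the PedsQL: "Parent-proxy reports for younger children and self-reports for older participants, mirroring the PSQI administration". It gives no age cut.

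Section 5 sets the age range: "This study will enroll Chinese children aged 6 to 18 years, divided into three distinct groups based on their health status". No age matching or stratification is stated. Section 5.1 lets the cancer group report by self or by proxy, with no age rule. Section 8.2 tells children that taking part includes "answering questions about sleep through their parents/legal guardians or research staff".

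Section 6 has both patient groups complete the forms on the ward, with same-day collection by the study team. Healthy children's forms come back through their parents.

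Section 4.3.3 lists the variables to be collected: "age (in years), gender, socioeconomic status (SES), disease type, disease status, and use of hypnotics (yes/no". Respondent and help are not on the list. Section 7 compares the groups by one-way ANOVA. Age, gender and SES enter only the secondary regression.

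**The concern.** A parent's report of a child's sleep and the child's own report are different measurements, and they may differ systematically. Ages 6-18 straddle the switch, so each group's mean PSQI is a mixture of the two. If the mixture differs between groups, part of any group difference is an informant difference.

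There are two routes to an unequal mixture:

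- **Age mix.** The healthy controls are siblings and staff children, and nothing holds their ages to those of the patients. A younger group has more parent-completed forms.
- **Help at 12-18.** Adolescents who are ill on a ward may get more help than healthy adolescents. The child still completes the form, but parent input may move the score.

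The comparison of prevalence above the cut-off of 5 uses the same score and is exposed in the same way. Section 4.3.3 itself says that age may influence sleep outcomes and calls for adjustment, yet the group comparison in section 7 names no covariate.

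**Working it through.** **What the protocol supplies.** It gives 50 children per group, ages 6-18, an example switch at 12, and a significance level of 0.05. It gives no PSQI standard deviation, no effect size, no power, no parent-self difference and no expected age mix. The inputs marked as assumed below are therefore assumptions.

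**1. Bias through age mix.** Bias = (difference in parent-completed share) × (parent-minus-self difference).

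- Assumed share difference: 20 to 40 percentage points. Assumed parent-self difference: 0.5 to 1.5 points.
- Low end: 0.20 × 0.5 = 0.1 points. High end: 0.40 × 1.5 = 0.6 points.
- The direction is unknown.

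**2. Scale.** By the normal approximation, the pairwise difference detectable with 80% power is (1.960 + 0.842) × √(2/50) = 0.56 SD. With an assumed SD of 3 to 3.5 this is 1.7 to 2.0 points. The high-end bias is 0.6/2.0 to 0.6/1.7, or about a third of it. The low-end bias is 0.1/2.0 to 0.1/1.7, or about 5 to 6%.

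**3. False-positive rate of the ANOVA.** Suppose there is no true group difference. A parent-self shift of 0.5 SD corresponds to 1.5 points at SD 3. The rejection probability comes from the noncentral F distribution with 2 and 147 degrees of freedom.

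| Parent-completed shares | Largest spurious difference | Rejection probability |
|---|---|---|
| Equal in all groups | 0 | 0.05 |
| 60/50/40% | 0.20 × 0.5 = 0.10 SD | 0.068 |
| 70/60/30% | 0.40 × 0.5 = 0.20 SD (0.6 points at SD 3) | 0.133 |

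Simulation (40,000 runs each) gives 0.065 and 0.136 for the two unequal cases.

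**4. How much age imbalance this needs.** Let u = (age − 12)/6, and let two groups have densities (1 − tu)/2 and (1 + tu)/2 on −1 to 1. Their under-12 shares are 0.5 ± t/4, so the share difference is t/2. Their mean ages differ by 6 × 2t/3 = 4t years. A 20-point difference needs t = 0.4 and a gap of 1.6 years. A 40-point difference needs t = 0.8 and a gap of 3.2 years.

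**5. What age adjustment recovers.**

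- With these tilted ages, the within-group slope of the under-12 indicator on u is −3/4. The younger group's mean u is lower by 2t/3, so the residual share difference after linear adjustment is t/2 − (3/4)(2t/3) = 0.
- With truncated-normal ages (SD 3 or 4, means moved 0.5 to 1.5 years each way), 0.1 to 4% of the bias remains.
- With an imbalance that jumps exactly at 12, 26 to 28% remains.
- An age-band term (6-11 v 12-18) is the switch itself. It removes this component entirely if the cut is followed and the parent-self difference is the same in each group.

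**6. Bias through help at 12-18.** This equals (share aged 12-18) × (difference in helped share) × (effect of help on the score). The protocol gives no figure for the last two. Age does not identify who was helped, and the 20 to 40 points in step 1 do not apply, because help does not change who completes the form.

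**The case against.** The strongest reply is that this is one openly stated age rule, identical for every group, and that proxy report for young children is a legitimate choice. Much of this stands, and it rules out several stronger readings.

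- **That the rule differs by group.** Section 4.2.1 makes no reference to group. What is loose is the example cut and the undefined help. What is uncontrolled is the resulting mix.
- **That the respondent can be neither checked nor adjusted for.** Age is recorded. If the 6-11/12-18 split is kept, the parent/child split follows from it. Only departures from the cut and help at 12-18 are lost. The forms themselves are not shown and may carry a respondent field.
- **That research staff are a fourth respondent.** Section 8.2 has children answer through parents or staff, so the child can still be the source. Section 6 gives staff the task of instruction.
- **That adjusting for linear age would fail.** Step 5 shows that it removes nearly all of the age-mix bias under ordinary imbalance. The gap is that the planned ANOVA has no age term at all.

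A statistical analysis plan could add that term. It could not recover help that was never recorded.

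The reply also has force against two remedies. A strict child-only rule from age 12 could lose data from ill adolescents. Respondent type as a main-model covariate would either duplicate age band or adjust for help that is itself a consequence of illness.

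**Conclusion.** The point holds in limited form. The respondent for the primary outcome changes within the age range on a loosely worded rule, the listed variables do not capture the respondent or help, and the stated ANOVA ignores age. A difference in age mix or in help would therefore pass into the group comparison.

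The age-mix component would be 0.1 to 0.6 PSQI points under the assumed inputs, from negligible to about a third of the detectable pairwise difference. It can be recovered from recorded age. The help component cannot be recovered or quantified from the protocol.

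A reader might infer that the primary comparison is biased. The document does not support that: bias needs both a parent-self difference and an unequal mix, and neither is given. The point deserves action because the remedy is cheap and the recording has to be in place before data collection.

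**What to change.** 1. Make 6-11 parent and 12-18 child, with help allowed, the firm rule for both questionnaires and all three groups. Align sections 4.2.2, 5.1 and 8.2 with it.
2. Add a tick-box to each form for who answered: parent, child alone, child with parent help, or child with staff help. Add the item to section 4.3.3.
3. In section 7, put age band (6-11 v 12-18) in the primary group comparison in place of the unadjusted ANOVA, and show the group contrasts within each band.
4. Report respondent and help by group. Use help only in a sensitivity analysis, for example restricted to unassisted adolescents, and not as a main-model covariate.

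The cost is one form item and one residual degree of freedom (147 to 146). The within-band contrasts will be imprecise: with an even split of 25 per group and band, the detectable difference is 2.802 × √(2/25) = 0.79 SD, against 0.56 SD overall. They should be presented as estimates with intervals.
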